4.1 Inclusion criteria

- Age 50-80
- Ever-smokers (current or previous)
- MDT diagnosis of ILD detected through lung cancer screening or through a non-screening pathway
- Attending the regional ILD clinic

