4.2 Exclusion criteria

- Unable to complete self-report questionnaire measures e.g. due to cognitive impairment or English not first language

- Unable to provide written informed consent.

Individuals who do not consent to participation in this study will not be disadvantaged in anyway. They will continue to receive ILD clinic assessment, treatment and follow-up as per standard practice.

5 Study Design

4.1 Screening service: Invitation letters, endorsed by GPs to improve participation ^{46,72,73}, were sent to all individuals (n=16, 402), age 55-74, registered at participating GP practices (n=14), asking ever smokers to attend a community-based Lung Health Check (LHC). The LHC, which took place in supermarket carparks in deprived areas of Manchester, assessed symptoms, lung cancer risk (PLCO_{m2012}) and measured spirometry. All participants with a 6-year lung cancer risk >1.5% were offered entry into the screening programme (n=1,450), which involved a non-contrast low dose CT scan at baseline and 12 months later. The first screening round was in 2016 and the second and final screening round in 2017.

4.2 Screening LDCT scans: All LDCT scans (Optima 660, GE Healthcare) use helical acquisition of axial images from lung apices to the costophrenic angles. Imaging is performed without intravenous contrast, in suspended maximal inspiration, with the patient supine and arms above head (scan time 5-10 seconds). Acquisition parameters (kVp and mAs) vary with body weight to achieve a CT dose index below 3.0 millisieverts. Images are reconstructed at 1.25 mm thickness and at 1.25 mm increments. Most CT scans are reported within 2 weeks by practising National Health Service (NHS) Consultant Radiologists with a specific interest in thoracic radiology.

4.3 ILD MDT: Any ILAs detected on screening LDCT scans were highlighted in the CT report and referred to the regional ILD MDT for review and discussion. The MDT consisted of three ILD respiratory physicians, a thoracic radiologist with an interest in ILD, two specialist ILD nurses and an MDT co-ordinator. Once discussed at the MDT, those deemed to have changes suggestive of significant ILD have been referred to the regional ILD service for assessment in the clinic.

4.4 Study population: Individuals attending the regional ILD clinic as a 'new referral' will be invited to participate. Inclusion and exclusion criteria will be evaluated and suitable participants will be provided with a

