patient information sheet (PIS) prior to written consent being obtained for enrolment into the study. We will recruit patients from two groups:

- **Group 1:** ILD diagnosed through the Manchester early detection of lung disease pilot (lung cancer screening programme) and
- **Group 2:** age and sex matched individuals with ILD diagnosed through standard non-screening pathway.

Participation at the clinic will involve collection of demographic information, medical history including co-morbidities and medication history, full lung function tests (within 6 weeks), shuttle-walk test (within 6 weeks), MDT outcome proforma, clinic visit outcome including initiation of any treatments and completed questionnaires.

6 Data storage and analysis

Data will be stored on a specially designed research database and analysed using SPSS. The original signed consent form and completed questionnaire are stored within a secured location accessible only to the research team at MFT. Statistical significance will be set at <0.05 . Clinical and demographic data analyses will be descriptive. Questionnaire scores will be calculated according to corresponding scoring algorithms, and mixed-modelling will be used to examine the changes in the various scores between the three time-points, explore factors associated with HRQOL and differences between Group 1 and Group 2.

7 Adverse events

It is not anticipated that any adverse outcomes will occur; direct study participation will only be on the day of clinic visit.

8 Quality assurances

Data entry will be the responsibility of all members of the research team who will check data control as a matter of standard practice.

9 Ethical considerations

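### The screened group comes only from a pilot sited in deprived areas, and nothing in the matching or analysis controls for deprivation in the comparison with routine-care ILD

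*Combined protocol and SAP*

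**What the plan says.** Section 5 (4.4 Study population) defines two groups. Group 1 is "ILD diagnosed through the Manchester early detection of lung disease pilot (lung cancer screening programme) and" Group 2 is "age and sex matched individuals with ILD diagnosed through standard non-screening pathway". Both are recruited from new referrals to the regional clinic.

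Section 5 (4.1 Screening service) describes where Group 1 originates. Invitations went to people "age 55-74, registered at participating GP practices (n=14", and ever-smokers among them were asked to come to a health check "which took place in supermarket carparks in deprived areas of Manchester". Those above a 6-year lung cancer risk of 1.5% were offered screening CT (1,450 people).

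Section 4.1 (Inclusion criteria) applies to both groups: age 50-80, ever-smoker, an MDT diagnosis of ILD by either route, and "Attending the regional ILD clinic". It sets no condition on practice, residence or deprivation.

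The data list in section 5 (4.4) includes demographic information but does not itemise it. Section 6 says clinical and demographic data will be described, and that a mixed model will examine questionnaire scores, including factors related to health-related quality of life and the difference between groups. It names no adjustment covariate.

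**The concern.** Comparing screened with routinely diagnosed patients is the whole of the secondary objective (section 3.1.2), and section 1.4 notes that no direct comparison of this kind has been made. Its results will be read as showing what earlier detection does to symptoms, quality of life, lung function and treatment.

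Route of diagnosis is linked by design to where patients live: one group comes through a few practices and sites in deprived areas, the other through a regional clinic. If deprivation differs between the groups and is related to the outcomes, part of any observed difference belongs to deprivation and not to the route. Matching on age and sex does not deal with this. Without a deprivation measure, a reader of the results could not tell whether a real difference had been hidden or an apparent one created.

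**Working it through.** The plan states no sample size, effect size, SD or deprivation distribution, so there is no planned figure to reproduce. The check has two parts.

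**1. The two sources side by side**

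| Feature | Group 1 | Group 2 | Source |
|---|---|---|---|
| Entry route | Manchester pilot only | Routine referral to the regional clinic | Section 5 (4.4) |
| Practices | 14 participating practices | No restriction | Section 5 (4.1); section 4.1 |
| Area | Health checks held in deprived areas | No restriction | Section 5 (4.1); section 4.1 |
| Age | Invited at 55-74 | 50-80, then matched | Section 5 (4.1, 4.4); section 4.1 |
| Sex | As found | Matched | Section 5 (4.4) |
| Smoking | Ever-smoker | Ever-smoker | Section 4.1 |
| Deprivation | Not measured by name | Not measured by name | Section 5 (4.4); section 6 |

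Age and sex are handled by matching and ever-smoking by eligibility. Deprivation is handled by none of eligibility, matching, named data or named model terms.

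**2. Illustration of size (assumed inputs, not from the documents)**

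Treat deprivation as present or absent, with no true effect of route. Then

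d = (share deprived in Group 1 − share deprived in Group 2) × effect of deprivation on the score, in SD units.

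The chance of a nominally significant group difference, with n per group, unit SD, a normal approximation and two-sided 5% (section 6 gives 0.05 but not the sidedness), is

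Φ(d/√(2/n) − 1.96) + Φ(−d/√(2/n) − 1.96).

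For a scale of n, apply the prevalences quoted in section 1.4 to the 1,450 people offered screening:

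- IPF: 1,450 × 6/449 = 19.4
- fibrotic abnormalities: 1,450 × 19/884 = 31.2
- fibrotic plus mixed: 1,450 × 34/884 = 55.8

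Hence n = 20, 30 and 55. Other figures in section 1.4 would widen this (2/692 gives 4.2; 86/884 gives 141.1), and only those who reach the clinic and consent would count.

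| Share deprived, Group 1 v Group 2 | Effect (SD) | d (SD) | n = 20 | n = 30 | n = 55 |
|---|---|---|---|---|---|
| 60% v 50% | 0.2 | 0.02 | 5.0% | 5.1% | 5.1% |
| 60% v 50% | 0.3 | 0.03 | 5.1% | 5.2% | 5.3% |
| 60% v 50% | 0.5 | 0.05 | 5.3% | 5.4% | 5.8% |
| 70% v 40% | 0.2 | 0.06 | 5.4% | 5.6% | 6.1% |
| 70% v 40% | 0.3 | 0.09 | 5.9% | 6.4% | 7.6% |
| 70% v 40% | 0.5 | 0.15 | 7.6% | 8.9% | 12.3% |
| 90% v 30% | 0.2 | 0.12 | 6.7% | 7.5% | 9.6% |
| 90% v 30% | 0.3 | 0.18 | 8.8% | 10.7% | 15.7% |
| 90% v 30% | 0.5 | 0.30 | 15.8% | 21.3% | 35.0% |

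Worked line: d = (0.90 − 0.30) × 0.5 = 0.30; with n = 55, √(2/55) = 0.191 and 0.30/0.191 = 1.573, so the rate is Φ(−0.387) + Φ(−3.533) = 0.350.

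The table sets Group 1 as the more deprived. If the shares are swapped, d changes sign and the rates stay the same. The formula treats the groups as independent and of equal size; the matching ratio is not stated.

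**The case against.** The strongest reply is that a deprivation gap is inferred, not shown. The protocol says where the health checks stood. It gives no deprivation data for the practices, for Group 1 or for the clinic, and it does not define the clinic's catchment. Section 1.3.1 reports that lower socio-economic status went with lower participation in another UK screening study, so attenders may be less deprived than their area. Section 1.2 describes Manchester as having the highest premature death rate in the country, and the clinic is held there (section 9.2), so routine referrals may be deprived too. All of this stands. It removes any claim about direction or size, but leaves the fact that the plan neither measures nor controls for a factor tied to its sampling.

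A second reply is that demographic information is already collected and the model will explore factors related to quality of life, so deprivation could be examined. It could, but it is not named, and exploring correlates is not the same as committing to an adjusted group difference.

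Some stronger readings are tempting and are not supported:

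- A reader might infer that the 50-80 criterion against invitation at 55-74 biases the comparison. Group 2 is age matched, so the design largely removes that contrast. At most, some patients without a counterpart might be consented, and an age range says nothing about deprivation.
- A reader might take Group 2 to be the whole regional clinic. It is limited to new referrals who are ever-smokers with an MDT diagnosis, and it is matched.
- A reader might conclude that the bias must run against screening. Section 1.3.1 leaves the direction open.

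**Conclusion.** The point holds as an uncontrolled, design-linked risk of confounding in the secondary comparison. It does not hold as a demonstrated bias. Over the assumed range (shares deprived from 60% v 50% to 90% v 30%, effect 0.2 to 0.5 SD), the spurious difference is 0.02 to 0.30 SD. The matching false-positive rates at a nominal 5% are about 5-16% with 20 per group, 5-21% with 30 and 5-35% with 55. The documents cannot narrow this range, and they give no SD with which to turn it into points on any questionnaire. The primary objective, the prevalence of ILD in the screening programme (section 3.1.1), makes no use of Group 2 and is untouched. This is an inexpensive improvement to the secondary analysis, not a flaw that undermines the study.

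**What to change.** In section 5 (4.4), add an area deprivation index derived from each participant's postcode to the data collected. Section 9.3 already provides for review of medical records for study purposes. Storing the index under the study number, without the postcode, keeps to the coding described in section 9.2.

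In section 6, state that the index will be reported by group, and that Group 1 versus Group 2 differences will be shown adjusted for it beside the unadjusted ones. For questionnaire scores this is one further term in the planned model. Lung function and treatment are only to be described as section 6 stands, so say there how their adjusted differences will be obtained; where numbers are too few for a model, tabulate by level of the index. Deprivation generally precedes the route of diagnosis, so adjusting for it should not remove an effect of screening. Reporting the distribution by group first shows whether the groups overlap enough for adjustment to mean much.

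The cost is one derived variable and one model term, with some loss of precision if the sample is small.

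Two other remedies may suggest themselves but are better avoided. An upper age limit for Group 2 would duplicate the matching and would need an interval from invitation to clinic visit that the documents do not give. Preferring Group 2 patients from the same practices could add selection bias: everyone aged 55-74 there was invited, so routine-route patients of that age would tend to be non-attenders, people below the risk threshold, or cases that screening missed.

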9.1 Patient protection

The principal investigator (PI) will ensure that this study is conducted in agreement with the Guidelines for Good Clinical Practice after appropriate ethical review and approval.

9.2 Subject confidentiality

Each participant's completed questionnaire and consent form will be stored in a locked filing cabinet in a secure location in the North West Lung Centre at Manchester University NHS Foundation Trust (MFT). This is where the regional ILD clinic is held. Patients recruited to the study have a unique study number. Data both clinical and laboratory will be coded according to the unique study number and not linked directly to patient identifiable information. The research database is hosted on a secure MFT network with access limited to the research team.

9.3 Informed consent

All participants will be asked to provide written informed consent (signed and personally dated by the patient) to study participation. This will take place during their first visit to the regional clinic. Patient data collected as part of the study is kept strictly confidentiality, but medical records may be reviewed for study purposes by authorized individuals other than their treating physician.

10 Administrative responsibilities

The study will be administered by the research team directly with oversight from the R+D department at MFT.

10.1 Amendments

Ethical approval covers only the information contained in the protocol. It does not include extensions or amendments to the study. All amendments need to be signed by the PI. Amendments will be communicated to the patients within the scope of the patient information / informed consent.

